20.0 Withdrawal of Subjects

N/A: This study is not enrolling subjects. This section does not apply.

20.1 Describe **anticipated** circumstances under which subjects may be withdrawn from the research without their consent.

Response: Pregnancy, DKA, severe and frequent hypoglycemia and drug intolerance (severe nausea and/or vomiting) developing any of the exclusionary condition listed in the inclusion and exclusion criteria.

The principal investigator of the study can remove a participant from the research study without their approval if for any reason he/she feels is appropriate, including: severe side effect, injury or medical condition which may place the patient at risk of further complications if patient continues to participate, failure to take the medication as instructed, failure to keep your scheduled appointments, cancellation of the study by the sponsor, or other administrative reasons.

Participation in this research study is voluntary. Subjects have the right to refuse to participate or to withdraw from participation at any time for any reason. Refusal to participate or withdrawal from the study will involve no penalty or loss of entitled benefits, nor affect the subjects ongoing medical care

20.2 Describe any procedures for orderly termination.

NOTE: Examples may include return of study drug, exit interview with clinician. Include whether additional follow up is recommended for safety reasons for physical or emotional health.

Response: If a subject withdraws from the research, the data collected to that point will be used toward the research finding. If applicable the subject will have to bring back any unused research drug and or device. If necessary, they will be asked to complete an end of study visit for their safety.

20.3 Describe procedures that will be followed when subjects withdraw from the research, including retention of already collected data, and partial withdrawal from procedures with continued data collection, as applicable.

Response: If a subject withdraws from the research, the data collected to that point will be used toward the research finding. Patients are allowed to withdraw from some procedures while continuing to participate in the study (take study medication). Efficacy and safety data will continue to be collected for the parts of study that patients agree to participate in.

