2.0 Scientific Endpoints

2.1 Describe the scientific endpoint(s), the main result or occurrence under study.

NOTE: Scientific endpoints are outcomes defined before the study begins to determine whether the objectives of the study have been met and to draw conclusions from the data. Include primary and secondary endpoints. Some example endpoints are: reduction of symptoms, improvement in quality of life, or survival. Your response should **not** be a date.

Response: **Primary endpoint:** Change from baseline in HbA1c at 26 weeks as compared to placebo. **Secondary endpoints:** Change from baseline as compared to placebo in a)fasting and postprandial blood sugars, mean weekly glucose concentrations, standard deviation of weekly blood sugars and fructosamine; b)fasting and postprandial glucagon and C-peptide concentrations; c)insulin doses; d)indices of oxidative and inflammatory stress in MNC, plasma and adipose tissue; e)oxidative and inflammatory stress in plasma

and MNC following meal challenge; f)subcutaneous fat mass, hepatic fat content and visceral fat mass; g)waist circumference, blood pressure, triglycerides, HDL cholesterol and incidence of metabolic syndrome; h)gastric emptying; i) 24 hour blood pressure; j) flow mediated dilatation in brachial artery, k) SF-36 score; l) depression (PHQ) score.

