10.0 Procedures Involved

10.1 Provide a description of **all research procedures or activities** being performed and when they are performed once a subject is screened and determined to be eligible. Provide as much detail as possible.

NOTE: This should serve as a blueprint for your study and include enough detail so that another investigator could pick up your protocol and replicate the research. For studies that have multiple or complex visits or procedures, consider the addition of a schedule of events table in in your response.

Response:

Screening Visit: Consent will be explained and signed. Fasting labs before 10:00am include; CBC, CMP, HbA1c, lipid panel, C-peptide and GAD-6 and a urine pregnancy test. Physician preformed physical and medical history, including; blood pressure, height and weight. Blood samples of patients with negative GAD-65 antibodies will be screened for islet cell antibodies, if patient had evidence of auto- immunity to beta cells in the past, they will be retested during screening. Patients with no evidence of autoimmunity to beta cells will not be included in this trial.

Study Visit day -14: After screening visit, qualifying patients will see a registered dietitian who will review their carbohydrate counting and diet and make an assessment of their calorie and carbohydrate intake. Then they will be seen by a CDE for instructions on

injection technique and CGM insertion. The patients will be blinded to CGM. Patients who have been using CGM prior to enrolling in the study can continue to use their CGM's (unblinded). All subjects will be advised to monitor their capillary blood glucose by fingerstick before and 2 hours after each meal and to wear their CGM constantly for a week. The subjects will also be asked to keep a diary of their food intake for a week to measure their calorie intake. Study subjects will not change the type of glucose meter during the trial. They will have their body composition measured by DEXA and MRI prior to the next visit. Smoking patients will be asked not to change their smoking habits during the study.

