17.0 Data Management and Analysis

17.1 Describe the data analysis plan, including any statistical procedures. This section applies to both quantitative and qualitative analysis.

Response: The focus of the proposed research is to evaluate the effect of liraglutide on mean HbA1c% over the period of 26 weeks of treatment. The similarities between the study groups, baseline values for subject's demographics and study endpoints will be compared using appropriate parametric tests. Transformations of the data in order to meet statistical assumptions may be considered. The **primary endpoint** of the study is to detect

a difference in HbA1c after 26 weeks of treatment with Liraglutide or placebo. The statistical analysis will be carried out using analysis of covariance (ANCOVA) and tested at the 0.05 level. Change in weight will be a covariate. The results will be computed as mean \pm SD. Analysis will be carried out on the basis of intention to treat (with last observation carried forward).

The secondary end points based on glycemic changes will include the difference from baseline in mean weekly glucose concentrations, standard deviations of the mean weekly glucose concentrations, HbA1c, fructosamine, the duration of time spent in hyperglycemia ($>150\text{mg/dl}$, $>200\text{mg/dl}$, $>250\text{mg/dl}$) and hypoglycemia ($<70\text{mg/dl}$, $<40\text{mg/dl}$), insulin dosage. A reduction in the AUC following the meal will constitute another secondary end point. Between groups comparisons of the magnitude of change from baseline will also be made for these glycemia related secondary endpoints using student's t-test. Comparisons for these and the primary endpoints will also be made using the paired t-test or Wilcoxon's test for paired data within each group.

The other secondary end-points of the study will be change from baseline after 26 weeks of treatment in the fasting and postprandial blood sugars, glucagon and C-peptide concentrations, indices of oxidative and inflammatory stress in MNC, plasma and adipose tissue; subcutaneous fat mass, hepatic fat content and visceral fat mass; features of metabolic syndrome; gastric emptying, blood pressure, vascular analysis, patient reported nausea, quality of life and depression scores. Between groups comparisons will be made using students t-test or ANCOVA (adjustment will be done for baseline differences). Within group comparisons for these endpoints will be made using paired t-test or Wilcoxon's test or ANCOVA.

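### Removal from the research for non-adherence or missed visits (20.1) leaves week 26 HbA1c uncollected, so intention to treat rests on a carried-forward value that may be an on-drug week 12 result

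*Combined protocol and SAP*

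**What the plan says.** Section 20.1 gives the principal investigator a broad power: "The principal investigator of the study can remove a participant from the research study without their approval". Among the listed reasons are "failure to take the medication as instructed, failure to keep your scheduled appointments". The list is open-ended and also covers administrative reasons. Pregnancy, ketoacidosis, severe and frequent hypoglycaemia and drug intolerance are named separately, as anticipated grounds for withdrawal.

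On what follows a withdrawal, sections 20.2 and 20.3 say: "If a subject withdraws from the research, the data collected to that point will be used toward the research finding". Section 20.2 adds a conditional exit visit: "If necessary, they will be asked to complete an end of study visit for their safety". It names no HbA1c and no week 26 timing. Section 20.3 describes one route for partial participation: "Patients are allowed to withdraw from some procedures while continuing to participate in the study (take study medication". It then says that efficacy and safety data go on being collected for whatever parts a patient still agrees to.

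The primary endpoint in section 2.1 is "Change from baseline in HbA1c at 26 weeks as compared to placebo". Section 17.1 states the analysis rule: "Analysis will be carried out on the basis of intention to treat (with last observation carried forward". In section 10.1, HbA1c is listed at screening ("Fasting labs before 10:00am include; CBC, CMP, HbA1c, lipid panel, C-peptide and GAD-6 and a urine pregnancy test"), at week 12 and at week 26, and at no other visit.

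**The concern.** An intention-to-treat comparison needs the outcome of every randomised patient, whether or not the patient kept injecting. Section 20.1 allows follow-up to end because of behaviour after randomisation, in people who have not withdrawn consent and who may be willing to give a week 26 sample. A patient who stops injecting but would still attend has no described route for doing so.

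The carry-forward rule then fills the gap from a sparse schedule. Only one HbA1c lies between screening and week 26, so a single on-drug reading can stand in for a value that would have been measured off drug. Once the draw has been missed, no analysis can recover it.

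**Working it through.** **Inputs.** Planned difference 0.35 HbA1c points and residual SD 0.5 (section 17.2); 42 patients per arm (section 4.1); HbA1c at screening, week 12 and week 26 (section 10.1). The documents give no rate of non-adherence, of missed visits or of removal.

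**The plan's own figure.** With two-sided alpha 0.05 (assumed, because sidedness is not stated) and 80% power, n per arm = 2 × [0.5 × (1.960 + 0.842) / 0.35]² = 32.04. This agrees with the stated 32. It is used here only as the source of the 0.35 and the 0.5.

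**What is carried forward, by time of removal.**
- Before week 12: only the screening value exists. If it is carried, change from baseline is zero by construction.
- Between weeks 12 and 26, on drug at week 12 and stopped later: the week 12 on-drug value is used as the week 26 value.
- Removed for missing week 8, 16 or 20: no HbA1c was due at the missed visit, yet the week 26 value is lost.

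**Size, as an illustration.** Assume that the full 0.35 is present at week 12, that the placebo mean does not move (so placebo removals have no effect), and that covariate adjustment is ignored. Let f be the share of the liraglutide arm removed after week 12, g the share removed before week 12, and r the fraction of the effect still present at week 26 in a patient who stopped.

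- Carried-forward estimate: 0.35 × (1 − g)
- As-randomised week 26 difference: 0.35 × [1 − f − g + r(f + g)]
- Overstatement: 0.35 × [f(1 − r) − g × r]

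With g = 0 and r = 0 (all removals late, effect wholly lost):

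| f | patients of 42 | carried-forward | as randomised | overstatement | relative to as randomised |
|---|---|---|---|---|---|
| 0% | 0 | 0.35 | 0.35 | 0 | 0% |
| 5% | 2.1 | 0.35 | 0.3325 | 0.0175 | 5.3% |
| 10% | 4.2 | 0.35 | 0.315 | 0.035 | 11.1% |
| 15% | 6.3 | 0.35 | 0.2975 | 0.0525 | 17.6% |

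If all of the effect is kept off drug (r = 1), late removals cause no overstatement. With f = g = 10% and r = 0.5, the two terms cancel: 0.35 × (0.05 − 0.05) = 0. Early removals alone (f = 0) give no bias if r = 0 and an understatement otherwise. For scale, the standard error of the difference with 42 per arm is 0.5 × √(2/42) = 0.109, so the largest entry in the table is about half a standard error.

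**The case against.** The best defence is that section 17.1 defines its analysis as intention to treat with carry-forward, so removed patients remain in the comparison as randomised. That stands. A reader might infer that 20.1 flatly contradicts 17.1, but the documents do not go that far: the analysis set is intact, and what is lost is the week 26 measurement. Removal is also discretionary, so it may be rare, and outcome loss after withdrawal is not confined to these two reasons.

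Four other stronger readings are tempting and are not supported.
- **Loss of power.** Under the carry-forward rule these patients still contribute a value, so counting them as lost describes a completers' analysis that is not planned. The 30% dropout in 17.2 may already include them.
- **More removals on liraglutide because of nausea.** Section 10.2 places nausea mainly at initiation and dose escalation, and section 10.1 aims to complete escalation in the first 4 weeks. Nausea-related non-adherence would then fall mostly before week 12, where the upward bias does not arise. Drug intolerance is a separate ground in any case. Nothing in the documents shows an excess of later removals in that arm.
- **Conflict between 20.1 and 20.3.** Declining a procedure, such as the fat biopsy, is not the same as failing to attend, so the two rules can hold together.
- **A ban on later data.** Sections 20.2 and 20.3 say that earlier data will be used; they do not say that nothing else may be. The closing sentence of 20.3 could be read generously, but the sentence before it ties continued participation to taking study medication.

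It is also fair that some patients who persistently miss visits will not supply a week 26 sample whatever the protocol says, and that attendance has a safety purpose because insulin is reviewed at visits. Neither is a reason to stop asking for the primary outcome.

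**Conclusion.** The point holds as a gap in outcome collection that works against the intention-to-treat aim. The mechanism follows from the text alone: removal from the research is allowed for non-adherence or missed visits, no later HbA1c is provided for, and the only post-baseline value that can be carried is from week 12.

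The size is not known. The range of 0 to 0.053 HbA1c points rests on an assumed 0 to 15% of late stoppers in the liraglutide arm, the full effect at week 12 and its complete loss by week 26. Applying the same arithmetic to the whole 30% dropout in 17.2 would give 0.35 × 0.30 = 0.105, but the documents do not say that dropouts are of this kind or that they occur after week 12. Early removals can offset or reverse the direction. This is worth correcting because it is cheap and cannot be repaired at analysis; the documents do not show that it would decide the result.

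**What to change.** Deleting the two reasons from 20.1 would not be enough, because the open-ended discretion would remain. Separate the end of outcome collection from the other consequences of removal:

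- In 20.1, state that non-adherence, missed appointments and administrative reasons are not grounds for ending outcome collection.
- In 20.3, state that patients who stop study drug or miss visits, and who have not withdrawn consent, are still asked to attend for the scheduled week 12 and week 26 HbA1c.
- In 17.1, state that the measured value is analysed in the randomised arm whether or not the patient was taking study drug, and that carry-forward applies only where no value can be obtained.

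Decisions on study drug and safety withdrawals are unchanged. The cost is protocol wording and a few additional draws that are already in the schedule. The downside for the sponsor is that off-drug values will count, so the estimated effect may be slightly smaller.

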21.0 Risks to Subjects

21.1 List the reasonably foreseeable risks, discomforts, hazards, or inconveniences to the subjects related to their participation in the research. Consider physical, psychological, social, legal, and economic risks. Include a description of the probability, magnitude, duration, and reversibility of the risks.

NOTE: Breach of confidentiality is always a risk for identifiable subject data.

Response:

Subjects who experience severe nausea or vomiting after starting liraglutide will discontinue the study. Those with mild or moderate nausea will continue for at least one more week. If they continue to experience significant nausea (defined as interfering with normal activities), they will discontinue the study.

Subjects who develop pancreatitis will be withdrawn from the study.

Subjects who develop a new thyroid tumor during the study will be withdrawn. Patients will be informed that they should let study investigators know if they develop any swelling in the neck.

For the entire duration of the study, the patients will maintain a diary to record any hypoglycemia and other untoward side effects like nausea, changes in appetite and other experiences. Patients will be instructed to call the Diabetes Center to speak to a study investigator directly in case of any problem or untoward side effects. They will be specifically asked to call if they have hypoglycemia (blood sugar <70 mg/dl) or hyperglycemia (blood sugar >250 mg/dl) on more than one occasion. The target blood glucose during the study will be between 70-180mg/dl at all times, without increasing the incidence of blood glucose < 70 mg/dl.

The following Information from the boxed warning in the package insert regarding the risk of thyroid c-cell tumors will be discussed in details with all participating subjects:

"Liraglutide causes dose-dependent and treatment-duration-dependent thyroid C-cell tumors at clinically relevant exposures in both genders of rats and mice. It is unknown whether Liraglutide causes thyroid C-cell tumors, including medullary thyroid carcinoma (MTC), in humans, as human relevance could not be ruled out by clinical or nonclinical studies. Liraglutide is contraindicated in patients with a personal or family history of MTC and in patients with Multiple Endocrine Neoplasia syndrome type 2 (MEN 2). Based on the findings in rodents, monitoring with serum calcitonin or thyroid ultrasound was performed during clinical trials, but this may have increased the number of unnecessary thyroid surgeries. It is unknown whether monitoring with serum calcitonin or thyroid ultrasound will mitigate human risk of thyroid C-cell tumors."

In addition, the following FDA text regarding the risk of developing fibrosarcomas will be discussed with all participating subjects

"In a 2-year repeat subcutaneous dose carcinogenicity study of liraglutide injected once a day in CD-1 mice, a treatment-related increase in fibrosarcomas was seen on the dorsal skin and subcutis, the body surface used for drug injection, in males in the 3 mg/kg/day group. These fibrosarcomas were attributed to the high local concentration of drug near the injection site. The liraglutide concentration in the clinical formulation (6 mg/mL) is 10 times higher than the concentration in the formulation used to administer 3 mg/kg/day liraglutide to mice in the carcinogenicity study (0.6 mg/mL)".

21.2 Describe procedures performed to lessen the probability or magnitude of risks, including procedures being performed to monitor subjects for safety.

Response: For the entire duration of the study, the patients will maintain a diary to record any hypoglycemia and other untoward side effects like nausea, changes in appetite and other experiences. Patients will be instructed to call the Diabetes Center to speak to a study investigator directly in case of any problem or untoward side effects. They will be specifically asked to call if they have hypoglycemia

(blood sugar <70 mg/dl) or hyperglycemia (blood sugar >250 mg/dl) on more than one occasion. Insulin doses will be titrated to target blood sugars between 70-180 mg/dl at all times without increasing the incidence of blood glucose < 70mg/dl. The following Information from the boxed warning in the package insert regarding the risk of thyroid c-cell tumors will be discussed in details with all participating subjects.

21.3 If applicable, indicate **which procedures** may have risks to the subjects that are currently unforeseeable.

Response: Any adverse effects of Liraglutide that are not currently known or those unique to their use in Type 1 diabetes may be some of the unforeseeable risks.

21.4 If applicable, indicate which research procedures may have risks to an embryo or fetus should the subject be or become pregnant.

Response: Not applicable, we will not be enrolling pregnant participants or who may become pregnant or within child bearing years without signing the consent stating they will use at least two forms of birth control. If a participant becomes pregnant they will be withdrawn from the study immediately

21.5 If applicable, describe risks to others who are not subjects.

Response: Not applicable, there is no risk to others not participating in this study

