Study Visit day 0: Subjects will come fasting for this visit. Each subject will be given one injection of Liraglutide 1.2 mg or placebo. A fructosamine and blood samples will be collected at baseline. Blood samples will be collected after the baseline at 30, 60, 120, 180, 240 and 300 minutes after the injection. (**This is being done to evaluate the acute effect of a single injection of Liraglutide on oxidative stress and inflammatory mediators, before any adjustments of insulin dose or effect of Liraglutide on blood glucose and weight is evident**). Subjects will be instructed by the study staff in the dosing and administration of the study medication. They will start Liraglutide injection at a dose of 0.6 mg per day or placebo injection on the following day. We will adjust the doses of basal and bolus insulin to eliminate low blood sugars(less than 70 mg/dl). At all subsequent visits insulin doses will be titrated to target blood sugars between 70-180 mg/dl at all times. Patients will return to the center after 7 days.

Study Visit week 1: Blood glucose concentrations will be reviewed. Insulin dose will be adjusted at the discretion of the study investigator to optimize blood sugar control as per

the targets mentioned above. Patients will be advised to increase the Liraglutide dose to 1.2 mg a day if they are able to tolerate the 0.6 mg dose. If they are experiencing mild nausea, subjects will continue with 0.6 mg daily for another 7 days. Those with severe nausea/vomiting will be dropped from the study. All other subjects will return in 7 days.

Study Visit week 2: Blood glucose concentrations will be reviewed. Insulin dose will be adjusted if needed. Subjects taking 0.6 mg dose and experiencing significant nausea will be dropped from the study. Subjects on 1.2 mg and experiencing significant nausea will decrease the dose to 0.6 mg and continue that dose for the duration of the study. Subjects on 1.2mg and experiencing mild nausea will continue on 1.2 mg for 2 more weeks. Subjects on Liraglutide 1.2mg daily without any gastro-intestinal side-effects will be asked to increase the dose to 1.8 mg daily. Study drug will be dispensed for additional 2 weeks.

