Study Visit week 4: Subjects will be asked to bring in their used study pens and the pen that they are using so that study nurse can log in the amount of drug used. If needed, the dose will be increased. The goal in the first 4 weeks is to increase patient's liraglutide dose to maximum tolerated dose. Maximum dose of liraglutide will be 1.8 mg daily. Subjects experiencing mild nausea with 0.6 mg or 1.2 mg will continue at that dose in the study. Those with severe nausea/vomiting with 1.8mg will decrease their dose to 1.2 mg and continue that dose throughout the study. Blood glucose concentrations will be reviewed. Insulin dose will be adjusted if needed. CGM will be discontinued. Study drug will be dispensed to last till the next visit.

Study visit week 8: Subjects will be asked to bring in their used study pens and the pen that they are using so that study nurse can log in the amount of drug used. Blood glucose concentrations will be reviewed. Insulin dose will be adjusted if needed. Study drug will be dispensed to last till the next visit.

Study Visit week 12: Subjects will be asked to bring in their used study pens and the pen that they are using so that study nurse can log in the amount of drug used. Blood glucose concentrations will be reviewed and vascular activity will be performed. Insulin dose will be adjusted if needed. Fasting blood, research labs, HbA1c, fructosamine, lipid panel, urine pregnancy test and 24 hr urine will be collected. FMD and 24hr blood pressure will be studied. Study drug will be dispensed for additional 4 weeks.

Study Visit week 16 and 20: Subjects will be asked to bring in their used study pens and the pen that they are using so that study nurse can log in the amount of drug used. Blood glucose concentrations will be reviewed. Insulin dose will be adjusted if needed. Study drug will be dispensed for additional 4 weeks.

Study visit week 24: CGM will be inserted. They will have their body composition measured by DEXA and MRI prior to next visit.

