Study Visit week 26: Subjects will come fasting for this visit. Research labs, CBC, CMP, Lipids, HbA1c and fructosamine will be collected. Records of blood glucose concentrations monitored by finger-stick and CGM for the previous 14 days will be obtained to assess their glycemic control. They will undergo meal challenge test (described above) and a fat biopsy. 24 hr urine will be collected. FMD and 24hr blood pressure will be performed. After this visit, subjects will be discharged from the study.

Blood samples (collected in protease and DPP-IV inhibitors) will be appropriately processed and assayed for glucose, C-peptide, glucagon, GLP-1 and gastric inhibitory peptide (GIP) which is also called gastric insulinotropic peptide, Reactive oxygen species (ROS) generation, Thiobarbituric acid reducing substances (TBARS), urinary isoprostanate,

intranuclear nuclear factor kappa B (NFkB) binding, the expression and concentration of Toll like receptor-4 (TLR-4), tumor necrosis factor alpha (TNF α), Inhibitor kappa B (IkB α), Matrix metalloproteinase 9 (MMP-9), Suppressor of cytokine signaling-3 (SOCS-3), Protein kinase C (PKC β II), Phosphotyrosine phosphatase -1B (PTP-1B), Glycogen synthase kinase 3 beta (GSK-3 β), Inhibitor kappa kinase (IKK β), C-jun amino terminal kinase (JNK-1) and amount of Insulin receptor (IR- β) and p-IR β in MNC and plasma concentrations of C-reactive protein (CRP), Monocyte chemoattractant protein -1 (MCP-1), Plasminogen activator inhibitor -1 (PAI-1), TNF α and Regulated upon activation Normal T cell Expressed and Secreted (RANTES). Adipose tissue samples will be processed and analyzed for intranuclear NFkB binding, the expression and concentration of TLR-4, TNF α , IkB α , MMP-9, SOCS-3, PKC β II, PTP-1B, GSK-3 β , IKK β , JNK-1 and amount of IR- β and p-IR β .

Clinical and Laboratory Procedures

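### Section 21.1 takes patients with severe nausea or vomiting out of the study at any dose, while the week 4 visit in Section 10.1 keeps those on 1.8 mg in at a lower dose

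*Combined protocol and SAP*

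**What the plan says.** Section 21.1 of the combined protocol and SAP sets this rule: "Subjects who experience severe nausea or vomiting after starting liraglutide will discontinue the study". Its only qualifier is that treatment has begun. It then lets patients with milder nausea go on for at least a further week, and ends participation if significant nausea persists. It contains no dose-reduction step.

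The visit schedule in Section 10.1 handles nausea by visit and dose:

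- Week 1, on 0.6 mg: "Those with severe nausea/vomiting will be dropped from the study".
- Week 2: significant nausea on 0.6 mg leads to removal. Significant nausea on 1.2 mg leads to a lower dose with the patient kept in. Escalation is also set here: "Subjects on Liraglutide 1.2mg daily without any gastro-intestinal side-effects will be asked to increase the dose to 1.8 mg daily".
- Week 4: "Those with severe nausea/vomiting with 1.8mg will decrease their dose to 1.2 mg and continue that dose throughout the study".

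Section 20.1 lists severe nausea and/or vomiting among the circumstances in which a subject may be withdrawn, with no dose limit.

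For the primary endpoint, Section 17.1 states: "Analysis will be carried out on the basis of intention to treat (with last observation carried forward".

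**The concern.** For a patient with severe nausea or vomiting on 1.8 mg, Section 21.1 and the week 4 visit are both mandatory in wording and give opposite outcomes. Two patients with the same event could be handled in opposite ways, each in line with the protocol.

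The case is foreseeable. Section 10.2 says that nausea and vomiting tend to occur at initiation and at dose escalation, and Section 10.1 makes the highest tolerated dose the goal of the first four weeks.

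Two consequences reach the analysis. First, the instruction followed determines whether the patient can supply a measured on-treatment HbA1c or is represented by a carried-forward value. Second, Section 19.9 counts events leading to withdrawal among the triggers for suspending the research, so the same clinical event may or may not add to that count.

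**Working it through.** **Step 1. Set the rules side by side.**

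| Place | Condition | Outcome |
|---|---|---|
| Section 21.1 | Severe nausea or vomiting, any time after starting | Leaves the study |
| Section 10.1, week 1 | Severe, on 0.6 mg | Leaves the study |
| Section 10.1, week 2 | Significant, on 0.6 mg | Leaves the study |
| Section 10.1, week 2 | Significant, on 1.2 mg | Dose lowered, stays in |
| Section 10.1, week 4 | Severe, on 1.8 mg | Dose lowered, stays in |
| Section 20.1 | Severe, any dose | May be withdrawn |

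Section 21.1 agrees with week 1 and conflicts with week 4. Section 20.1 is permissive, fits either reading and so does not settle the matter. There is also a softer mismatch at week 2. Significant nausea on 1.2 mg leads to a lower dose there, whereas Section 21.1 ends persistent significant nausea in discontinuation, though only after at least one further week.

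**Step 2. Can the conflicting case arise?** Escalation to 1.8 mg can happen at week 2. Week 4 − week 2 = 2 weeks of possible exposure to 1.8 mg before the week 4 visit. It can arise.

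**Step 3. Which HbA1c values exist under each instruction?** Section 10.1 lists HbA1c at three visits:

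- Screening: "Fasting labs before 10:00am include; CBC, CMP, HbA1c, lipid panel, C-peptide and GAD-6 and a urine pregnancy test"
- Week 12: "Fasting blood, research labs, HbA1c, fructosamine, lipid panel, urine pregnancy test and 24 hr urine will be collected"
- Week 26: "Research labs, CBC, CMP, Lipids, HbA1c and fructosamine will be collected"

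A patient removed at week 4 has 0 of the 2 scheduled on-treatment values. Section 20.2 provides an end-of-study visit where necessary but does not list its tests, so it may or may not supply a value. If it does not, the screening value is both baseline and last observation:

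analysed change = screening − screening = 0.00.

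A patient kept in could have values at both week 12 and week 26.

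**Step 4. Scale.** The documents give no expected number of patients with severe nausea or vomiting on 1.8 mg, so k below is illustrative. Inputs: 42 patients per arm (Section 4.1) and a planned difference of 0.35 HbA1c points (Section 17.2). Assumptions: a retained patient would show a 0.35-point change, all k patients are in one arm, and none has an HbA1c at a closing visit.

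Difference between the two instructions in the arm mean = k × 0.35/42. Share of the planned difference = k/42.

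| k | Shift in arm mean | Share of 0.35 |
|---|---|---|
| 1 | 0.35/42 = 0.008 | 1/42 = 2.4% |
| 3 | 1.05/42 = 0.025 | 3/42 = 7.1% |
| 5 | 1.75/42 = 0.042 | 5/42 = 11.9% |

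A smaller response at the lowered dose shrinks these figures in proportion. At half the response, for example, k = 5 gives 0.042/2 = 0.021.

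**The case against.** The best reply is that Section 10.1 is the operational plan and Section 21.1 is a summary of risks. A rule tied to a dose and a visit would normally be read as overriding a general sentence. The wording of Section 21.1 also suggests the start of treatment: its sequence (severe, out; milder, another week; still significant, out) follows the week 1 and week 2 rules for 0.6 mg. On that reading the fault is a summary sentence with its scope left out. This is plausible and may be what was intended. But Section 21.1 does not limit itself to the starting step, and no text gives Section 10.1 precedence.

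Second, Section 20.1 already gives the investigator discretion to withdraw a patient, and a single centre with weekly research meetings makes divergent handling less likely. Both points stand, and reconciling the sections would not remove that discretion. They reduce the practical risk, but they do not reconcile two mandatory instructions.

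Third, a zero change after loss before week 12 follows from the HbA1c schedule and last observation carried forward. It applies to every early dropout, including the undisputed removals at weeks 1 and 2. That is correct. The conflict does not create the problem; it leaves open which patients fall into it. The 30% dropout allowance in Section 17.2 covers numbers of patients and not this effect.

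Finally, the affected group is narrow and the values of k are chosen for illustration. That is accepted.

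**Conclusion.** The concern holds. For severe nausea or vomiting on 1.8 mg, Section 21.1 and the week 4 visit in Section 10.1 give opposite mandatory outcomes, the event can arise under the escalation scheme, and nothing in the document resolves the conflict.

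The numerical effect on the primary comparison is small unless several patients are affected, and its true size cannot be derived because the documents do not give the number of such patients. The illustrative figures are upper values under their assumption that a retained patient would show the full planned change and no more. The contradiction itself rests on the text alone and needs none of these assumptions. It should be corrected, chiefly because it decides who stays in the study and who can supply on-treatment HbA1c.

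**What to change.** Reconcile Section 21.1 with the week 1, week 2 and week 4 instructions in Section 10.1, so that a single instruction applies to severe nausea or vomiting at each dose step. If Section 21.1 is meant only for the starting step, say so there. Otherwise, state which section prevails. The same edit should settle the week 2 mismatch on significant nausea at 1.2 mg. Which clinical rule applies is for the investigator to decide.

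The cost is protocol wording only, with no added visits or procedures.
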